Aim 1 (Strategy 1): Modulating the limbic system as an approach to treatment: mPFC iTBS. Cigarette smokers will be randomized to receive 10 days of real iTBS or sham iTBS directed to the mPFC. Intermittently the desire to smoke, cigarette value using behavioral economic demand, preference for immediate gratification (delay discounting), and cigarette self-administration will be assessed. Smoking cue-evoked brain activity will also be measured when individuals are asked to 'crave' (passive limbic engagement) versus 'resist' the craving (executive engagement)(7,11-13). We hypothesize that iTBS will: 1) decrease the behavioral smoking measures described above, which will be explained by a selective 2) decrease in the neural response to cues when individuals 'allow' themselves to crave, and 3) sustain these changes over a time period sufficient to overcome the initial quit attempt (~7-14 days).

Aim 2 (Strategy 2): Modulating the executive system as an approach to treatment: dlPFC iTBS. Aim 2 will follow the design of Aim 1. The procedures will be identical, except iTBS will be delivered to the left dlPFC. We hypothesize that iTBS will: 1) decrease the behavioral smoking measures described above, which will be explained by a selective 2) increase in the neural response to cues when individuals attempt to 'resist' the cues, and again 3) sustain these changes over a similar period as specified in Aim 1.

Exploratory Aim- Evaluate baseline frontal striatal connectivity and discounting rate as factors to predict an individual's likelihood of responding to Strategy 1 versus Strategy 2. We will test the hypotheses that individuals with a higher ratio of (mPFC-striatal)/(dIPFC-striatal) connectivity will be more likely to have a behavioral change after Strategy 1. Various demographics (e.g. gender, smoking history, socioeconomic status, subclinical depressive symptoms, self-efficacy, & motivation to quit will be evaluated as explanatory variables.

The outcomes of the present aims will resolve a critical gap in our knowledge regarding the relative efficacy of 2 promising TMS treatment strategies. These outcomes will be directly translated to a larger longitudinal study evaluating a multipronged approach to improving outcomes in traditional pharmacotherapy or behavioral treatments.

Methods and Measures

Design

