Study Visit Procedures: At all visits, individuals will provide a urine screen to detect recent use of drugs of abuse and pregnancy, a breath carbon monoxide (CO) sample to detect recent cigarette smoking, and a breath sample to test for recent alcohol use. During the consent visit, visits 1, 6, 10 and follow up visits samples will be collected to determine cotinine (nicotine metabolites) levels in the urine. Samples will be taken from the urine sample provided for the drugs of abuse screen, no additional samples will be required from the participant. At visits 1, 6, 10 and follow up visits (Assessment visits), participants will complete a battery of behavioral assessments following active TMS or sham (see Table 2). MRI scanning (at visits 1 and 10) will occur prior to TMS in order to isolate cumulative, rather than acute, effects of TMS. At all visits participants will be required to provide a CO reading at least 50% of their baseline CO measure to ensure they are at least 6 hours deprived from cigarettes. Cigarette deprivation will be use to increase craving and responding for cigarettes. Short term cigarette deprivation has known amplification effects on the brain response to smoking cues (93, 94). Moreover, we have extensive experience with successfully using this deprivation procedure (33, 41).

Table 2 1. Biochemical and self-report assessment of tobacco use and dependence						
Measure	Time (Min.)	Visits	Description			
Carbon monoxide (CO Level)	1	1-10, and follow-ups	Breath CO provides an accurate measure of recent exposure to CO , including from smoking combustible tobacco products (95). The CO measurement will be used to determine recency of smoking.			
Timeline Follow-Back (TLFB) interview	5	1, 6, 10, and follow-ups	This self-reported tobacco product use interview asks participants to retrospectively estimate the number of tobacco products they've used each day for the past 30 days or since the previous assessment, whichever is fewer (89).			
Fagerström (FTND)	3	1, 6, 10, and follow-ups	This 6-item questionnaire quickly assesses degree of cigarette dependence (96, 97). Test for Cigarette Dependence.			
2. Measures of t	tobacco pr	oduct value an	d sensitivity (**PRIMARY DEPENDENT MEASURES)			

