Questionnaire on Smoking Urges-Brief (QSU)	2	1 - 10 and follow-ups	This 10-item questionnaire assesses cigarette craving . Participants will be asked to rate from 1 (strongly disagree) to 100 (strongly agree) their agreement with several statements (e.g., "I have a desire for a cigarette right now," and "Nothing would be better than smoking a cigarette right now."). Factor analyses support two factors: one that reflects a strong desire and intention to smoke and one that reflects relief from negative affect associated with an urgent desire to smoke (45).			
Hypothetical Purchase Task (**Demand Alpha, Q0) (HPT Cigarettes)	5	1, 6, 10, and follow-ups	The hypothetical purchase task (HPT), a validated measure for cigarette demand, (98, 99) will assess cigarette purchases at various price conditions. Participants will hypothetically purchase quantities of cigarettes to use over a 24-hour period across ascending prices (e.g., \$0, 0.12, \$0.25, \$0.50, \$1.00, and \$2.00 per cigarette). The HPT has been shown to be predictive of treatment outcomes (100).			
3. Cognitive/beha	vioral tasl	k (** PRIMAR	Y DEPENDENT MEASURE)			
Delay- discounting tasks (*discounting rate, \$1K)	5	1, 6, 10, and follow-ups	Participants will be asked to choose between two conditions in which varying amounts and delays to behavioral outcomes (e.g., \$50 now or \$100 later) are presented. We will use magnitudes of \$100 and \$1000 which are the most thoroughly documented among the literature (101). Across consecutive choices, the delay to the larger outcome will be titrated until reaching the participant's indifference delay (i.e., the delay at which s/he equally values both options). This indifference delay indexes individual participants' rates of delay discounting. [61]. Monetary delay discounting has been documented to be predictive to treatment success for smokers (39).			
1. Brain Reactivity to Smoking Cues (**PRIMARY DEPENDENT MEASURE)						

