Behavioral Outcomes: For the treatment phase (10 days of real/sham TBS), the primary behavioral outcomes include Cigarette demand (Q0 and alpha), Craving (QSU Intention, QSU Relief), and Delay Discounting (\$100 and \$1000). For the treatment phase the analysis will be performed using repeated measures ANOVA on change scores from baseline for each visit. The main independent variable in the ANOVA will be time (visits on day 1, 6, 10), group (real or sham) and their interaction. For correlations of observations across visits an AR(1) structure will be considered and compared with other structures such as compound symmetry and a general structure. The primary hypothesis is the interaction. If the interaction effect for an outcome is significant, we will conclude there is statistical evidence of overall treatment effect. If the spaghetti plots suggest trends (e.g., linear, quadratic, or piecewise changes) we will treat time as a continuous variable and fit repeated measures regression models along with group and its interaction with continuous time as independent variables.

Neuroimaging Outcomes: For the treatment phase, primary analysis. Image pre-processing will be conducted with FSL v. 5.0: (FMRIB Analysis Group, Oxford, UK) (108) realignment to the first volume, smoothing with an anisotropic 8-mm Gaussian kernel, high-pass filtering, resampling to 2-mm isotropic voxels, and stereotactic registration to the Montreal Neurological Institute 152-subject average template. Subjects with >3 mm movement (total mean frame displacement across the entire task) will be excluded from analysis.

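### The primary behavioural test is a group-by-time interaction on change scores with Day 1 as a level, but baseline is undefined; depending on the reading, one planned covariance cannot be fitted or a constant effect is missed

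*Combined protocol and SAP*

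**What the plan says.** Outcome Measure(s), Behavioral Outcomes, covers demand (Q0, alpha), craving (two QSU factors) and discounting ($100, $1000). It sets the treatment-phase analysis as follows: "For the treatment phase the analysis will be performed using repeated measures ANOVA on change scores from baseline for each visit". It continues: "The main independent variable in the ANOVA will be time (visits on day 1, 6, 10), group (real or sham) and their interaction". Then: "The primary hypothesis is the interaction", and "If the interaction effect for an outcome is significant, we will conclude there is statistical evidence of overall treatment effect". On covariance, "an AR(1) structure will be considered and compared with other structures such as compound symmetry and a general structure".

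Table 2 schedules demand and discounting at visits "1, 6, 10, and follow-ups", and QSU at Visits 1 to 10 and follow-ups. The screening battery (Experimental Procedure, Screening Visit) contains none of these measures. No section defines baseline for them.

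The timing within Visit 1 is inconsistent. Study Visit Procedures says that at assessment visits "participants will complete a battery of behavioral assessments following active TMS or sham". The same paragraph puts MRI before stimulation, and the fMRI row of Table 2 puts the scan after the behavioural assessments, which would place behaviour before stimulation. Sample Size uses four time points; the analysis model has three.

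The Aim 1 hypothesis is that stimulation will lower the behavioural measures and "sustain these changes over a time period sufficient to overcome the initial quit attempt".

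**The concern.** Two analyses are merged. On raw values at Visits 1, 6 and 10, the group-by-time interaction is the treatment effect. On change scores the baseline is already subtracted, and the treatment effect is the group difference at the post-baseline visits. An interaction among those visits answers a different question.

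This rule decides whether each primary behavioural outcome counts as positive. With baseline undefined, readings of the same sentence lead to very different tests, and the choice could be made after group labels are known: the interim plan gives the principal investigator unblinding codes at each 20% of enrolment. A multi-degree-of-freedom interaction also has no sign, so the rule as worded would count a Day 6/Day 10 crossover as an overall treatment effect.

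**Working it through.** **Inputs from the protocol.** Per Aim, 46 active and 23 sham (Analytical Plan); 108 usable data sets, so 54 per Aim, or 36:18 if 2:1 is kept; effect d = 0.8; type I error 5% (taken as two-sided). **Assumed:** raw SD 1 at each visit, and AR(1) correlation ρ = 0.5 (range 0.3 to 0.9), because the plan uses an observed correlation but does not give it.

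**The plan's own figure.** It states 28 per group for 80% power at d = 0.8. A simple two-sample t-test needs 26; 28 per group gives 83.6%. The stated basis (four time points, observed AR(1)) cannot be rerun without the correlation.

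**Reading A: baseline is Visit 1, Day 1 kept.** The Day 1 change is 0 for everyone, so the 3×3 covariance of the changes has a zero row and column (rank 2, determinant 0). The unstructured REML likelihood is unbounded: −2logL per df goes from −3.6 to −8.3 to −17.5 as the Day 1 variance goes from 10⁻² to 10⁻⁴ to 10⁻⁸. AR(1) and compound symmetry can be fitted, though their equal-variance assumption is false. Simulated type I error (46:23, 4,000 runs per setting) is 5.2–6.4% for AR(1) and 4.7–5.7% for compound symmetry, against 4.4–5.7% on raw scores.

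Power of the 2-df test, ρ = 0.5, effect 0.8 at Days 6 and 10:
- Var(Day 6 change) = 2(1 − 0.5) = 1; Var(Day 10 change) = 2(1 − 0.25) = 1.5; covariance = 0.5 − 0.5 − 0.25 + 1 = 0.75; determinant = 1.5 − 0.5625 = 0.9375.
- Noncentrality = 0.64 × (1.5 − 1.5 + 1)/0.9375 ÷ (1/n₁ + 1/n₂) = 0.6827 ÷ 0.06522 = 10.47 at 46:23, and 0.6827 ÷ 0.08333 = 8.19 at 36:18.
- Noncentral F (2 and N − 3 df): 81.5% and 70.1%.

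Power of the 1-df contrast on the mean of the two changes:
- Variance = 0.25 × 1 + 0.25 × 1.5 + 0.5 × 0.75 = 1.0.
- Noncentrality = 0.8/√(1/n₁ + 1/n₂) = 3.13 and 2.77, giving 87.0% and 77.6%.

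The same contrast adjusted for baseline:
- Residual variance = 0.5(1 + 0.5) − [0.5(0.5 + 0.25)]² = 0.75 − 0.1406 = 0.609.
- Noncentrality = 0.8/√(0.609(1/n₁ + 1/n₂)) = 4.01 and 3.55, giving 97.7% and 93.6%.

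**Reading B: Day 1 dropped.** With Visits 6 and 10 only, the interaction tests the Day 10 minus Day 6 difference. For a constant effect that contrast is 0.8 − 0.8 = 0, so power equals alpha, 5.0%, at every ρ.

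**Reading C: separate pre-stimulation baseline, Days 1, 6 and 10 all post-baseline.** The interaction tests whether three group differences are equal. A difference constant over all three gives contrasts of 0, so power is again 5%. An effect that grows after Day 1 would still be picked up.

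**Power at ρ = 0.5 by effect pattern:**

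| Effect at Days 6, 10 (SD) | N | 2-df, Day 1 kept | Day 1 dropped | Mean change, 1-df | Mean, baseline-adjusted |
|---|---|---|---|---|---|
| 0.8, 0.8 | 46:23 | 81.5% | 5.0% | 87.0% | 97.7% |
| 0.8, 0.8 | 36:18 | 70.1% | 5.0% | 77.6% | 93.6% |
| 0.4, 0.8 | 36:18 | 48.9% | 27.5% | 53% | 74% |
| 0.8, 0.4 | 36:18 | 70% | 27.5% | 53% | 74% |

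The last two rows have the same mean effect, (0.8 + 0.4)/2 = 0.6, so the 1-df columns agree; the Day 10 minus Day 6 difference is ±0.4, so the dropped-Day-1 column agrees too. For either pattern at 46:23 the adjusted contrast has about 84%. For the sustained effect at 46:23, the 2-df and mean-change powers are 69.6% and 78.5% at ρ = 0.3, and 95.6% and 96.7% at ρ = 0.7.

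**The case against.** The plan names Day 1 as a time level, so dropping it departs from the text. With Day 1 kept, the interaction jointly tests the Day 6 and Day 10 differences. That is a legitimate treatment test; under compound symmetry its F statistic is the same as on raw scores. Only one of three candidate covariance structures fails. The omnibus test also beats the unadjusted mean-change contrast when the effect fades (70% against 53% at 36:18, ρ = 0.5; 92% against 71% at ρ = 0.7). All of this stands.

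It is also fair that a Day 1 change of zero is an inference from the schedule. A pre-stimulation assessment plus Days 1, 6 and 10 would give the four time points of Sample Size, and nothing would then be singular. But that reading does not rescue the rule, because Day 1 becomes a post-treatment visit and a constant effect is detected only at alpha.

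The Aim 1 wording does not predict equal effects at Days 6 and 10. Its period is about 7–14 days, Table 1 makes durability a secondary follow-up goal, and Neuroimaging Outcomes speaks of a dose-dependent relation. The constant-effect figures therefore describe one plausible pattern. On direction, any two-sided test can favour sham and the estimates would show it; the remaining gap is that the decision rule does not require the sign to be checked.

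**Conclusion.** The rule is faulty as written on each reading, but the size depends on the reading. If Visit 1 is baseline and Day 1 stays in, the promised covariance comparison cannot be completed. The cost is otherwise modest: 5.5 points at 46:23 (87.0 − 81.5) and 7.5 at 36:18 (77.6 − 70.1) for a sustained effect at ρ = 0.5, and less as ρ rises. If Day 1 is dropped, or a separate baseline makes it a post-treatment visit, a constant effect is found only 5% of the time.

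A reader might infer that the planned test cannot detect the predicted effect, or that it inflates false positives. The documents support neither. The 5% figure needs Reading B or C, and type I error with the zeros kept stays near nominal. Nor is Visit 1 certain to be the baseline; it is the only one the schedule lists.

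The figures rest on an assumed AR(1) correlation, equal raw SDs, no group difference at baseline and complete data at the stated sizes. This should be fixed, but it does not undermine the trial.

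**What to change.** 1. Define baseline for demand, craving and discounting. Reconcile Sample Size (four time points), Study Visit Procedures and Table 2 on whether the Visit 1 behaviour battery comes before or after the first session. If it comes after, any immediate effect of that session is subtracted out with the baseline.
2. In Behavioral Outcomes, do not use the baseline visit as an outcome level. Make the primary test one pre-named 1-df active-minus-sham contrast at the post-baseline visits: the mean of Visits 6 and 10, or one named visit. Use an unstructured covariance over those visits, and adjust for the baseline value if it is measured before the first session.
3. Report group-by-visit as secondary, and claim benefit only when the contrast favours active.

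The cost is wording; no new data are needed. One contrast must be named before unblinding, which under the interim plan means before codes are released at the first 20% of enrolment. A single contrast is also less sensitive than an omnibus test to some patterns. For a fading effect at 36:18 and ρ = 0.7, the adjusted contrast has 82.5% (residual variance 0.85 − 0.595² = 0.496; noncentrality 0.6/√(0.496 × 0.08333) = 2.95) against 92% for the 2-df test.

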Hypothesis Aim 1: Based on the framework predicted by CNDS theory, and preliminary work (see Study 4), we anticipate that mPFC stimulation will lead to a decrease in brain reactivity to cues during the "allow" condition (passive limbic engagement). We will analyze the neuroimaging data in concert with the behavioral data, evaluating the hypotheses that 1) mPFC iTBS will decrease the brain reactivity to cues in the 'allow' condition (with no consistent link to the 'resist' condition) and that 2) this will be related to the behavioral change in a dose-dependent manner. This will be achieved by extracting the average BOLD signal timecourse and the percent signal change during the CIG versus NEU blocks from a priori anatomically defined regions of interest (ROIs), including the striatum (ventral striatum and dorsal striatum), insula, inferior frontal gyrus, and anterior cingulate cortex. Ventral striatal and dorsal striatal ROIs are derived from the FSL Oxford-GSK-Imanova striatal atlas, mapped via probabilistic diffusion tractography (109) in agreement with anatomical projection zones from the frontal cortex (1). Hypothesis Aim 2: Based on the framework predicted by CNDS theory, and prior studies of dlPFC stimulation in smokers (4-9), we anticipate that dIPFC stimulation will lead to an increase in executive control circuitry (left dlPFC, posterior parietal cortex) during the "resist" condition (executive engagement). As in Aim 1, we will analyze the neuroimaging data in concert with the behavioral data, evaluating the hypotheses that 1) dIPFC iTBS will decrease the brain reactivity to cues in the "resist" condition (with no consistent link to the "allow" condition) and that 2) this will be related to the behavioral change in a dose-dependent manner. The ROI based outcomes of Aim 2 will be compared with the outcomes of Aim 1 using standard general linear modeling as well as a data-driven hierarchical model (see Integration below). As an experimental control, for both Aims we will also calculate the percent signal change from the primary motor cortex, a region which should not be differentially modulated by mPFC or dIPFC stimulation. Although some studies have used the visual cortex as a control region a recent meta-analysis by our group demonstrated that the visual cortex is typically activated more to drug cues than neutral cues (78). Secondary functional connectivity analysis: Additionally, an exploratory seed-based functional connectivity analysis using psychophysiological interactions (PPIs) will be performed using the TMS stimulated ROIs (mPFC and dlPFC) and the striatal target regions (ventral striatum, dorsal striatum- defined above) as seed regions. These data will be compiled across participants and compared between the mPFC and dIPFC stimulation days. Group analyses will be performed using a random effects model limiting significant clusters to those that meet p<0.05 family-wise error corrected.

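### Both Aims predict a selective brain effect in one task condition, but no test that the *allow* and *resist* conditions differ is specified, so an equal effect in both could be reported as selective

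*Combined protocol and SAP*

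**What the plan says.** The Objectives use the same phrase in both Aims: the behavioural change is one "which will be explained by a selective 2") neural effect. For Aim 1 that effect is a "decrease in the neural response to cues when individuals 'allow' themselves to crave". For Aim 2 it is an "increase in the neural response to cues when individuals attempt to 'resist' the cues".

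Outcome Measure(s), Neuroimaging Outcomes, restates this as hypothesis 1 of each Aim. Aim 1 predicts a decrease in "brain reactivity to cues in the 'allow' condition (with no consistent link to the 'resist' condition"). Aim 2 predicts that stimulation will "decrease the brain reactivity to cues in the 'resist' condition (with no consistent link to the 'allow' condition"). The stated means is extraction of percent signal change (CIG versus NEU) from a priori regions: ventral and dorsal striatum, insula, inferior frontal gyrus and anterior cingulate.

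The formal comparisons that are named answer other questions:
- Neuroimaging Outcomes: "The ROI based outcomes of Aim 2 will be compared with the outcomes of Aim 1".
- Behavioral Outcomes: a group-by-time interaction, for behavioural measures only.
- Exploratory Aim: a hierarchical model that lists caudate signal in both conditions, for predicting response and comparing the two strategies. It states no condition contrast.
- Analytical Plan: general chi-square, t-test or ANOVA group comparisons, and further analysis as appropriate.

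Table 2 gives each participant one *allow* run and one *resist* run at Visits 1 and 10, with run order fixed within subject and counterbalanced within groups.

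**The concern.** Selectivity is a statement about a difference: the real-minus-sham effect is larger in one condition than in the other. A significant result in one condition beside a non-significant one in the other does not establish that difference, and a non-significant result does not establish absence of a link. The plan offers an effect in the named condition plus no consistent link in the other. It gives no contrast between conditions and no equivalence margin. An analyst following it could call an equal effect selective.

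This matters because limbic (*allow*) against executive (*resist*) engagement is the mechanism that is meant to tell the two strategies apart. Table 2 marks cue reactivity as a primary dependent measure. The habit of inference is also already visible: the Figure 5 caption, on the pilot data, supports a real-versus-sham statement with within-group contrasts.

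**Working it through.** **The plan's own figure.** Sample Size gives 28 per group for d=0.8, 80% power and 5% type 1 error. A simple two-sided two-group comparison needs n = 2(1.96+0.84)²/0.8² = 24.5, so 25 per group (26 by t-test), close to 28. The plan's own method (four time points, AR(1)) cannot be rerun because the correlation is not given. No figure is stated for selectivity.

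**Inputs.** Two-sided alpha is 0.05 (sidedness is not stated, so this is an assumption). The 108 usable data sets give 54 per Aim, or 36:18 at 2:1. If the stated 10% imaging loss comes off after 78% retention, 138 × 0.78 × 0.9 = 96.9, about 48 per Aim, or 32:16. The correlation ρ between a participant's *allow* and *resist* change scores is not in the documents and is varied. Equal SDs in the two conditions are assumed.

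**Step 1: equal true effect, one region.** Let Z1 and Z2 be the real-versus-sham statistics in the named and the other condition, bivariate normal with common mean δ and correlation ρ. Here δ = 1.96 + z(power), which is 1.96 at 50% power and 2.80 at 80%. The false selective pattern has probability P(Z1 > 1.96, |Z2| ≤ 1.96). At ρ=0 this is p(1−p): 0.5 × 0.5 = 25% and 0.8 × 0.2 = 16%. Dividing by p gives the share among trials significant in the named condition.

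| ρ | Pattern, 50% power | Pattern, 80% power | Share, 50% power | Share, 80% power |
|---|---|---|---|---|
| 0 | 25% | 16% | 50% | 20% |
| 0.5 | 17% | 11% | 33% | 14% |
| 0.7 | 13% | 9% | 25% | 11% |

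At 36:18 with d=0.8 in both conditions, the pattern has probability 16.5%, 11.6%, 8.9% and 5.1% at ρ = 0, 0.5, 0.7 and 0.9. Simulated t-tests (40,000 runs) give 17.5%, 12.2% and 9.6% at the first three.

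**Step 2: the direct test.** Compare arms on the within-person *allow*-minus-*resist* change. With equal effects it rejects 5% of the time two-sided, so about 2.5% in the claimed direction. Requiring it together with the pattern of Step 1 leaves about 1.2-2.3% false selective findings (simulation, 36:18, ρ 0 to 0.7, d 0.5 or 0.8).

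**Step 3: five regions.** Take ρ=0.5 and assume correlations between regions of 0.3-0.7. The Step 1 pattern then appears in at least one region in about 29-39% of trials at 80% power and 41-53% at 50%. The direct test, unadjusted, gives at least one false result in the claimed direction in about 7-10% of trials (1 − 0.975⁵ = 12% for independent regions), so it also needs multiplicity control.

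**Step 4: power of the direct test.** The SD of the within-person difference is √(2(1−ρ)), in units of the single-condition SD. Two-sample t-test, unadjusted:

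| ρ | 36:18, d 0.8 vs 0 | 36:18, d 0.8 vs 0.4 | 32:16, d 0.8 vs 0 |
|---|---|---|---|
| 0 | 49% | 16% | 44% |
| 0.3 | 63% | 21% | 58% |
| 0.5 | 78% | 28% | 73% |
| 0.7 | 94% | 42% | 91% |

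For comparison, the single-condition test for d=0.8 has 78% power at 36:18.

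**The case against.** The parenthesis about no consistent link sits inside a hypothesis. The plan never says that a non-significant result in the other condition will count as evidence. A reader might infer that the sponsor has adopted a significant-here, not-there rule. The text does not go that far: it leaves the criterion open. *Link* may also mean association with behaviour, since imaging is to be analysed together with the behavioural data. That is fair, but it does not remove the gap. On that reading the two brain-behaviour slopes would have to be compared, and no such comparison is stated either.

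The Exploratory Aim's hierarchical model could hold a condition contrast, and the Aim 2 text points to a hierarchical model under a heading, Integration, that is not in the supplied text. Nothing in the model as described states such a contrast. It names only the caudate, which would not cover the insula, inferior frontal gyrus, cingulate or ventral striatum.

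A reader might also infer that the trial's main conclusions are at risk. The primary hypotheses in the Design section are lower cue reactivity in the salience network and lower cigarette value, with mPFC stimulation the more efficacious. Selectivity by condition is not among them. An error here would misstate the mechanism, not the real-versus-sham result on behaviour or cue reactivity.

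**Conclusion.** The gap is real and narrow: a mechanistic claim made in both Aims has no specified test. Under equal true effects, one region would look selective in about 9-25% of trials. That is 11-50% of the trials that are significant in the named condition, against about 2.5% for a direct test. These ranges rest on 50-80% power per test and an assumed between-condition correlation of 0 to 0.7. A higher correlation shrinks the problem, but it still exceeded 2.5% at 0.9. Across five regions the chance in at least one is roughly 29-53%, under the correlations assumed above.

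Two stronger statements should be avoided. Treating the five regions as independent gives 45-60% (1 − 0.887⁵ and 1 − 0.833⁵), but regions of one brain are correlated, and the plan does not say that a single region would suffice for the claim. Nor is the direct test free in power: it matches the single-condition test only if the correlation is about 0.5 or more and the other condition has no effect. This should be corrected because correction is cheap, not because the primary comparisons depend on it.

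**What to change.** In Neuroimaging Outcomes, for each Aim, specify a test of arm by condition (*allow*, *resist*) on the Visit 1 to Visit 10 change in regional percent signal change (CIG minus NEU), with participant as random effect and run order as covariate. Claim selectivity only if both of these hold:
- the active-minus-sham effect in the named condition is significant in the hypothesised direction;
- the arm-by-condition term is significant in that direction.

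The first condition is needed because the interaction alone could arise from a change in the other condition. Adjust for multiplicity across the a priori regions, or pre-name one region or composite. Otherwise report the active-minus-sham effect in each condition with its confidence interval and make no selectivity claim.

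Before this can be applied to Aim 2, its direction must be reconciled. The Objectives predict an "increase in the neural response to cues when individuals attempt to 'resist' the cues", and the Aim 2 text also anticipates an increase in executive-control regions under *resist*, while its hypothesis 1 predicts a decrease in reactivity to cues there. If different regions are meant, the plan should say so.

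The cost is wording, since both runs are already scheduled at each scan. The downside is a claim that is harder to make. Power to meet both conditions cannot exceed the lower of the two tests' powers (at 36:18, 78% for the first and the Step 4 figures for the second). Multiplicity adjustment lowers it, as will the unquantified number of participants who skip MRI for COVID-related reasons.
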